## **6 ENDPOINTS AND COVARIATES**

### **6.1 EFFICACY ENDPOINTS**

All efficacy endpoints in this study are considered CCI ( see section 6.3).

### **6.2 SAFETY ENDPOINTS**

All AE/SAE data will be summarized, including (but not limited to) the safety concerns detailed in Table 1 Summary of Ongoing Safety Concerns to be Assessed in THAOS: hepatotoxicity, changes in thyroid function (particularly in pregnancy); reproductive and developmental toxicity and lactation.

Safety endpoints include the incidence of AEs and SAEs, change from baseline in laboratory parameters and change from baseline in vital signs.

For interventional clinical trials that include open-label tafamidis or other open label investigational products, patients may continue in THAOS, but data collected for such patients (if included in the THAOS database) will be excluded from all safety analyses specified within this SAP.

#### **6.2.1 Survival**

Survival will be analysed as time from enrollment or first dose of tafamidis, for the untreated and tafamidis treated set respective until the time of death. Patients who are still alive at the end of the analysis period (start of tafamidis or end of follow-up in THAOS for the untreated set or last dose of tafamidis in the tafamidis treated set) will be censored.

CCI [Redacted]

[Redacted]

[Redacted]

[Redacted]

- [Redacted]
- [Redacted]
- [Redacted]

CCI [Redacted]

[Redacted]

[Redacted]

[Redacted]

PFIZER CONFIDENTIAL

[Redacted]

CCI

[Redacted]

[Redacted]

[Redacted]

CCI

[Redacted]

[Redacted]

[Redacted]

[Redacted]

[Redacted]

CCI

[Redacted]

[Redacted]

PFIZER CONFIDENTIAL

[Redacted]

CCI [Redacted]

CCI [Redacted]

[Redacted]

[Redacted]

[Redacted]

[Redacted]

[Redacted]

[Redacted]

- [Redacted]
- [Redacted]
- [Redacted]
- [Redacted]

PFIZER CONFIDENTIAL

[Redacted]

CCI [Redacted]

[Redacted]

[Redacted]

[Redacted]

- [Redacted]
- [Redacted]
- [Redacted]
- [Redacted]
- [Redacted]
- [Redacted]

[Redacted]

- [Redacted]
- [Redacted]

[Redacted]

[Redacted]

CCI [Redacted]

[Redacted]

[Redacted]

[Redacted]

CCI [REDACTED]

CCI [REDACTED]

CCI [REDACTED]

[REDACTED]

[REDACTED]

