#### **5.1 ALL ENROLLED**

This analysis set will include patients who have been enrolled in THAOS study and have signed the informed consent form.

The enrollment date will be considered as the date when informed consent form (ICF) was signed.

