## 5.3 TAFAMIDIS TREATED

The tafamidis treated set will include the following:

[figure not shown]
- All available data from the enrollment date until final treatment discontinuation of tafamidis or end of follow-up in THAOS (whichever is earlier) for patients who have been enrolled in THAOS, signed the informed consent and who were on tafamidis treatment on or prior to the date of enrollment in THAOS.
- All available data from first dose of tafamidis until final treatment discontinuation of tafamidis or end of follow-up in THAOS (whichever is earlier) for patients who were not on tafamidis at the time of enrollment in THAOS but subsequently initiated treatment with tafamidis.

Note: A patient can be considered part of both the tafamidis untreated and tafamidis treated sets if the patient initiated treatment with tafamidis after beginning participation in THAOS.

The below schematic will help to better understand the patient population to be analysed:

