### 8.2.4 Symptoms

The ongoing definitely related symptoms at enrollment/baseline, ongoing possibly related symptoms at enrollment/baseline, and ongoing symptoms at enrollment/baseline unrelated to TTR will be summarized by severity for the following sets: tafamidis treated set by phenotype at enrollment and overall, tafamidis untreated set by phenotype at enrollment and overall, and tafamidis treated set who are either predominantly cardiac or mixed phenotype at enrollment by CCI class at enrollment.

The past definitely related symptoms at enrollment/baseline, past possibly related symptoms at enrollment/baseline, and past symptoms at enrollment/baseline unrelated to TTR will be summarized by severity for the following sets: tafamidis treated set by phenotype at enrollment and overall, tafamidis untreated set by phenotype at enrollment and overall.

Symptoms developed post enrollment/baseline (defined as a symptom with an onset date after the date of enrollment for the untreated set and as a symptom with an onset date after the first dose of tafamidis for the treated subset) will be summarized by severity separately based on whether or not symptoms were definitely related, possibly related, or unrelated to TTR for the following sets: tafamidis treated set by phenotype at enrollment and overall, tafamidis untreated set by phenotype at enrollment and overall, tafamidis treated set who are either predominantly cardiac or mixed phenotype at enrollment by CCI class at enrollment, tafamidis treated set for patients who switched from predominantly cardiac to mixed phenotype, tafamidis treated set for patients who switched from predominantly neurologic to mixed phenotype, tafamidis untreated set for patients who switched from predominantly cardiac to mixed phenotype, tafamidis untreated set for patients who switched from predominantly neurologic to mixed phenotype.

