### 8.2.6 Safety Analyses

#### Survival Analyses

Mortality will be analysed using the Kaplan Meier method with median survival times (if estimable) and 95% CIs if the number of events are at least 5.

Mortality will be summarized and presented by plots for the following sets: tafamidis treated set by phenotype at enrollment and overall, tafamidis untreated set by phenotype at enrollment and overall, CCI and either predominantly cardiac or mixed phenotype at enrollment, tafamidis treated set for patients who had severe hepatic impairment at baseline, tafamidis

untreated set by their liver transplantation status (liver transplant prior to enrollment/liver transplant after enrollment/no liver transplant), tafamidis treated set by liver transplantation status (liver transplant prior to first dose of tafamidis/liver transplant after the first dose of tafamidis/no liver transplant).

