## APPENDIX 2: DATA DERIVATION DETAILS

### A1.1 Definition and use of visit windows in reporting

For All enrolled set and tafamidis untreated set (as well as the subgroups corresponding to untreated set), Day 1 will be the most recent available value collected either on or after the informed consent signed date. The study day will be calculated as follows:

Study day = assessment date – consent date

For the tafamidis treated set (as well as the subgroups corresponding to treated set), Day 1 will be the most recent available value collected either on or after the first dose of tafamidis received after enrollment in THAOS. The study day will be calculated as follows:

Study day = assessment date – date of first dose of tafamidis after enrollment in THAOS / consent date if patient was continuing taking tafamidis prior to enrollment (whichever is earlier) + 1

The following visit window will be applied, considering the absolute value of study day (absday):

Condition	Visit	Year
$\text{absday} < -365.25 \times 0.5$	-1	
$0 \leq \text{absday} \leq 365.25 \times 0.5$	0	
$365.25 \times 0.5 < \text{absday} \leq 365.25 \times 1.5$	1	1
$365.25 \times 1.5 < \text{absday} \leq 365.25 \times 2.5$	2	2
$365.25 \times 2.5 < \text{absday} \leq 365.25 \times 3.5$	3	3
$365.25 \times 3.5 < \text{absday} \leq 365.25 \times 4.5$	4	4
$365.25 \times 4.5 < \text{absday} \leq 365.25 \times 5.5$	5	5
$365.25 \times 5.5 < \text{absday} \leq 365.25 \times 6.5$	6	6
$365.25 \times 6.5 < \text{absday} \leq 365.25 \times 7.5$	7	7
$365.25 \times 7.5 < \text{absday} \leq 365.25 \times 8.5$	8	8
$365.25 \times 8.5 < \text{absday} \leq 365.25 \times 9.5$	9	9
$365.25 \times 9.5 < \text{absday} \leq 365.25 \times 10.5$	10	10
$365.25 \times 10.5 < \text{absday} \leq 365.25 \times 11.5$	11	11
$365.25 \times 11.5 < \text{absday} \leq 365.25 \times 12.5$	12	12

Note: If study day is missing, then visit will be considered as missing.

CCI [REDACTED]

	CCI [REDACTED]	[REDACTED]	[REDACTED] → [REDACTED]
CCI [REDACTED]	[REDACTED]	[REDACTED]	[REDACTED]
[REDACTED]	[REDACTED]	[REDACTED]	0 → 4 1 → 3.75 2 → 3.5 3 → 3.25 4 → 2 5 → 0
[REDACTED]	[REDACTED]	[REDACTED]	Present → [REDACTED] [REDACTED] → [REDACTED]
[REDACTED]	[REDACTED]	[REDACTED]	Normal → [REDACTED] Decreased → [REDACTED] Absent → [REDACTED]
CCI [REDACTED]	[REDACTED]	[REDACTED]	[REDACTED]

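### SAP 6.2.1 starts treated-set survival at an unqualified first dose, so for patients already on tafamidis at enrolment a literal reading counts time in which no death could be recorded

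*SAP*

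**What the plan says.** SAP 6.2.1 sets the origin: "Survival will be analysed as time from enrollment or first dose of tafamidis, for the untreated and tafamidis treated set respective". It makes no exception for patients who started the drug before entering THAOS. Those still alive at "last dose of tafamidis in the tafamidis treated set) will be censored".

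SAP 5.3 includes in the treated set patients "who were on tafamidis treatment on or prior to the date of enrollment in THAOS". What is used for them is "All available data from the enrollment date until final treatment discontinuation of tafamidis or end of follow-up in THAOS (whichever is earlier"). SAP 5.1 fixes that date: "The enrollment date will be considered as the date when informed consent form (ICF) was signed".

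The estimator, in the survival part of SAP 8.2.6, is conventional: "Mortality will be analysed using the Kaplan Meier method with median survival times (if estimable) and 95% CIs". Neither 8.1 nor 8.2.6 mentions delayed entry, left truncation or a separate origin for established users.

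SAP Appendix 2 does treat these patients separately. Their study day runs from the "consent date if patient was continuing taking tafamidis prior to enrollment (whichever is earlier) + 1". That rule is written for study day and visit windows, not for survival.

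**The concern.** A patient who had taken tafamidis for three years before consent enters the 6.2.1 analysis with three years of survival already credited. Had that patient died in those years, there would be no record in THAOS. The interval adds to the number at risk but cannot add a death, so the estimated hazard is too low at every time when such patients are counted. The untreated clock starts at enrolment and gains no such time.

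SAP section 2 says the safety data will give information on the effect of tafamidis on survival. SAP 8.2.6 plans treated-set mortality overall, by phenotype, by transplant status and in severe hepatic impairment. All of those curves and medians would carry the same defect.

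The time bases would also differ within 8.2.6. Exposure is counted only while the patient is enrolled, so a mortality rate per patient-year built on that exposure would not use the same follow-up as the Kaplan-Meier curve.

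**Working it through.** The documents give no survival figure, event count or sample size, so there is no plan figure to reproduce.

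**1. The text.** Let F be the date of first dose, E the consent date and X the exit date, with F before E. Section 6.2.1 gives a survival time of X − F. Section 5.3 observes the patient only from E to X. Ordinary Kaplan-Meier counts the patient at risk from time 0, so E − F is included although no death in it is observable. SAP Table 2 has a tafamidis log with start dates, completed at baseline and at optional retrospective visits, so a programmer could compute X − F.

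**2. Size under assumptions.** None of these inputs is in the documents:
- mortality h = 0.10 per year, constant;
- a share p of the treated set already on drug at enrolment, with lead time uniform on 0 to 4 years;
- follow-up after enrolment (or after first dose, for new users) uniform on 0 to 8 years.

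Put G(u) = exp(−hu)(1 − u/8). At time t since first dose (t up to 4 years), those counted at risk are:
- new users: N = (1 − p)G(t);
- established users who have enrolled: B = (p/4) × integral of G from 0 to t;
- established users not yet enrolled: C = p(1 − t/4).

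Deaths come only from N + B. The literal reading therefore estimates the hazard h × w(t), with w = (N + B)/(N + B + C), and 3-year survival of exp(−h × integral of w from 0 to 3).

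For p = 0.5:
- w(0) = 0.500
- w(1) = (0.396 + 0.112)/(0.396 + 0.112 + 0.375) = 0.575
- w(2) = (0.307 + 0.199)/(0.307 + 0.199 + 0.250) = 0.669
- w(3) = (0.232 + 0.266)/(0.232 + 0.266 + 0.125) = 0.799

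By the trapezoid rule the integral is 0.250 + 0.575 + 0.669 + 0.400 = 1.89, and exp(−0.189) = 0.828. The true value is exp(−0.30) = 0.741.

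| Share already on drug | True 3-year survival | Literal 6.2.1 | Overstatement (points) |
|---|---|---|---|
| 10% | 74.1% | 75.9% | 1.9 |
| 25% | 74.1% | 78.6% | 4.5 |
| 50% | 74.1% | 82.8% | 8.7 |
| 75% | 74.1% | 86.7% | 12.6 |

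(Overstatements are taken before rounding.) At p = 0.5, mortality of 0.06 per year gives 89.1% against 83.5%, and 0.20 gives 69.6% against 54.9%. A simulation of 1,000,000 patients per case agrees with these figures. If the 0 to 4 year lead is instead assigned to everyone who starts the drug, and those who die before consent are then removed, the 75% case gives 85.4%, an overstatement of 11.3 points.

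**3. Whether the two repairs agree.** With constant mortality, delayed entry and an enrolment origin both return 74.1%. With rising mortality they separate. Take survival from first dose as exp(−(0.12t)^k), p = 0.5 and the same lead and follow-up (simulated):

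| k | True 3-year, from first dose | Literal 6.2.1 | Delayed entry | Enrolment origin |
|---|---|---|---|---|
| 1.5 | exp(−0.216) = 80.6% | 86.5% | 80.6% | 75.9% |
| 2 | exp(−0.1296) = 87.8% | 91.3% | 87.8% | 81.0% |

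Delayed entry recovers survival since treatment start. The enrolment origin answers another question: survival from enrolment in a mix of new and established users.

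**The case against.** The strongest reply is that 6.2.1 never says the clock starts before enrolment. It applies to a set whose data, for these patients, begin at enrolment. Appendix 2 uses the consent date for continuing users, the column labels in 8.2.8 for the transplant subgroups refer to a first dose in the study, and exposure is counted only while enrolled. First dose in 6.2.1 may therefore be shorthand for first in-study dose, in which case no unobservable time is added. This stands as a possible intention. It does not settle the matter: the SAP writes the in-study qualifier elsewhere and omits it here, and the one explicit consent-date rule is confined to study day and visit windows. Either way 6.2.1 needs the sentence.

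The magnitudes also rest on inputs the documents do not supply. Data collection began in December 2007 and EU approval came on 16 November 2011, so nobody enrolled in roughly the first four years was already on EU commercial drug. From that approval to the planned end of data collection on 16 June 2023 is 11.6 years, which bounds the lead on EU commercial product but says nothing about its typical length. The cardiomyopathy approvals listed in Protocol 7.1 date only from March 2019, so the effect may differ widely by phenotype.

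A reader might infer that 8.2.4 has the same fault, since it defines later symptoms "as a symptom with an onset date after the first dose of tafamidis for the treated subset". The documents do not support that. SAP 8.2 sets the treated baseline within three weeks of starting tafamidis, so onset after first dose is post-baseline by the SAP's own definition. If starting means the in-study start, the difficulty does not arise.

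**Conclusion.** As written, 6.2.1 conflicts with 5.3 and, followed literally with ordinary Kaplan-Meier, overstates treated-set survival. The mechanism and its direction for the treated curve follow from the text. The size does not: 1.9 to 12.6 points on 3-year survival is an illustration for 10% to 75% already on drug, mortality of 0.10 per year and a lead of 0 to 4 years.

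A reader might go further and conclude that the SAP plans a treated-versus-untreated comparison that must favour tafamidis. The documents do not go that far. Section 4 states that there are no hypotheses and that all analyses are descriptive, 8.2.6 lists sets for plots without a test between them, and the only survival comparison among the objectives concerns liver transplant. The upward bias is established for the treated curve against a correctly truncated one, not for the net contrast with untreated patients, which has other sources of selection.

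**What to change.** Add one statement to SAP 6.2.1 choosing between:

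- (a) origin at first dose, with each patient entering the risk set at the later of first dose and consent (left truncation), reported as survival since treatment start; or
- (b) origin at the later of first dose and enrolment, matching 5.3 and Appendix 2, reported as survival from enrolment in a mix of new and established users.

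State which one applies, since they differ when mortality changes with time on drug. Under (a), show the number at risk over time, because few patients may be under observation early on the clock. Under either, reporting the number already on drug at enrolment and their lead times would let readers judge the mix.

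The cost is a sentence, one date derivation and, for (a), an entry-time argument in the Kaplan-Meier program. No new data are needed where start dates are already in the tafamidis log. If the literal reading was what the sponsor had in mind, treated survival will come out lower than it otherwise would. Neither repair removes every selection effect that comes with enrolling established users.

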## 5.2 TAFAMIDIS UNTREATED

The tafamidis untreated set will include the following:

- All available data from patients who have been enrolled in THAOS, signed the informed consent and who have not received tafamidis during the THAOS study.
- All available data before receiving the first dose of tafamidis while in THAOS, for those patients who were not on tafamidis during or after initial enrollment in THAOS but then started receiving tafamidis post enrollment.

Note: Available data after a patient discontinues treatment with tafamidis will be excluded (See Figure 1)

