## 7 HANDLING OF MISSING VALUES

Missing observations will be treated as missing except for dates. For dates with missing days but not missing months, the 1st of the month will be imputed, and for dates with missing months and days, July will be imputed for months and the 15th will be imputed for days.

For any missing data (CCI [REDACTED]) corresponding to PRO, the PRO specific scoring manual will be utilized for imputation.

Patients with missing data for a variable will be excluded from the denominator when calculating proportions involving observed data for that variable.

If the tafamidis start day is missing, it will be imputed as the 15th of the corresponding month as per the eCRF guidelines. For date of birth, if only year is collected, then the day and month will be considered as 1st of January.

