## **8 STATISTICAL METHODOLOGY AND STATISTICAL ANALYSES**

### **8.1 STATISTICAL METHODS**

The key objectives of the survey are to better understand the natural history of ATTR (hereditary and wild-type forms) and the progression of disease in this patient population. Analysis of clinical outcomes will be conducted on all enrolled patients with available data. Outcomes will be examined separately for the untreated and tafamidis treated sets, as well as for appropriate subgroups within these set. Outcomes will include results of the key clinical, functional and QoL assessments used to define progression of disease.

Data will be summarized descriptively.

Continuous variables will be summarized using descriptive statistics ie, number of non-missing values and number of missing values [ie, n (missing)], mean, median, standard deviation (SD), minimum, maximum and 10th and 90th percentile.

Qualitative variables will be summarized by frequency counts and percentages. Unless otherwise specified, the calculation of proportions will be based on non-missing values.

In case the analysis refers only to certain visits, percentages will be based on the number of patients still present in the study at that visit, unless otherwise specified. Sample size in a subgroup needs to be at least 10 in order to have sufficient data to provide descriptive statistics, listings will be provided for smaller subgroups.

Kaplan-Meier estimates (product-limit estimates) will be presented including the median time with two-sided 95% confidence intervals (CIs), if the number of events are at least 5.

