### **Exposure**

Duration of exposure (in years) among patients receiving tafamidis while enrolled in THAOS will be summarized (excluding time when the patient was part of clinical trial or Compassionate Use/Early Access Program) by starting dose using the tafamidis treated set by phenotype at enrollment and overall, CCI [REDACTED] and either predominantly cardiac or mixed phenotype at enrollment, tafamidis treated set for patients who had severe hepatic impairment at baseline, tafamidis treated set by liver transplantation status (liver transplant prior to first dose of tafamidis/liver transplant after the first dose of tafamidis/no liver transplant).

Additionally the duration of treatment with 20 mg and 61 mg/80 mg will be summarized separately for patients with off label use.

The duration of exposure (in years) will be calculated as:

Sum of all non-missing days when tafamidis was taken (excluding days of other clinical trial/compassionate use participation) / 365.25

Summary of exposure-adjusted Incidence rates (per patient-year) AEs and SAE for Treatment Emergent Adverse events (All causalities) and mortality for tafamidis treated set will be provided.

A separate listing will be provided for duration of exposure listing for patients who switched from 61/80 mg to 20 mg.

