### Deaths

Summaries on the number (%) of patients who died, by primary cause, and whether deaths were ATTR related will be provided using all enrolled patients, tafamidis treated set by phenotype at enrollment and overall, tafamidis untreated set by phenotype at enrollment and overall, CCI [REDACTED] and either predominantly cardiac or mixed phenotype at enrollment, tafamidis treated set for patients who had severe hepatic impairment at baseline, tafamidis treated set by liver transplantation status (liver transplant prior to first dose of tafamidis/liver transplant after the first dose of tafamidis/no liver transplant), tafamidis untreated set by their liver transplantation status (liver transplant prior to enrollment/liver transplant after enrollment/no liver transplant).

A separate listing of deaths will also be provided for the tafamidis treated set.

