### **Echocardiogram**

For Echocardiogram, summary statistics for the baseline will be provided for:

- Left atrium
- Aortic root
- LV septum
- LV posterior wall

- LV diastolic diameter
- LV systolic diameter
- LV ejection
- RV free wall thickness
- Quantitative LV end systolic volumes
- Quantitative LV end diastolic volumes
- Transmitral E wave peak velocity
- E wave deceleration time
- Transmitral A wave Peak velocity
- Peak tricuspid regurgitation velocity
- Derived peak pulmonary artery systolic pressure
- Septal and Lateral Peak E, A, S
- Stroke volume
- Cardiac output

Also for the following parameters corresponding to Echocardiogram, summaries will be provided at baseline:

- Value abnormalities
- Types of value abnormalities
- Respiratory variation
- Sparkling

Echocardiogram summaries will be performed for the following sets: tafamidis untreated set with predominantly cardiac or mixed phenotype at enrollment, tafamidis treated set with predominantly cardiac or mixed phenotype at enrollment, CCI [REDACTED] and either predominantly cardiac or mixed phenotype at enrollment, tafamidis treated set for patients who switched from predominantly neurologic to mixed phenotype and tafamidis untreated set for patients who switched from predominantly neurologic to mixed phenotype.

*Note: For all the above safety events (Concomitant medications, hospitalization, AE/SAE, Deaths, Laboratory, Vitals and ECG) all events collected till last tafamidis dosing date +28 days will be summarized for the tafamidis treated set and its associated sub-sets.*

CCI [REDACTED]  
[REDACTED]  
[REDACTED]  
[REDACTED]  
[REDACTED]  
[REDACTED]

PFIZER CONFIDENTIAL

CCI [Redacted]

CCI [Redacted]

[Redacted]

[Redacted]

[Redacted]

[Redacted]

[Redacted]

[Redacted]

[Redacted]

[Redacted]

PFIZER CONFIDENTIAL

[Redacted]

CCI [Redacted]

[Redacted]

CCI [Redacted]

[Redacted]

- [Redacted]
- [Redacted]
- [Redacted]
- [Redacted]
- [Redacted]
- [Redacted]
- [Redacted]
- [Redacted]
- [Redacted]
- [Redacted]
- [Redacted]

[Redacted]

CCI [Redacted]

[Redacted]

[Redacted]

CCI [REDACTED]

[REDACTED]  
[REDACTED]  
[REDACTED]

[REDACTED]  
[REDACTED]

[REDACTED]

[REDACTED]  
[REDACTED]  
[REDACTED]

[REDACTED]

[REDACTED]  
[REDACTED]  
[REDACTED]

[REDACTED]

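### Treated-set survival is cut at the last tafamidis dose while treated-set deaths are counted to 28 days after it; the SAP needs one end date for treated-set mortality

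*SAP*

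**What the plan says.** Four parts of the SAP set the time window for mortality in the treated set.

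- **Section 6.2.1 (Survival)** measures treated-set survival from first dose to death. It ends the analysis period at the last dose for patients still alive: "last dose of tafamidis in the tafamidis treated set) will be censored". No days are added.
- **Section 5.3 (Tafamidis Treated)** ends treated-set data at final discontinuation or end of THAOS follow-up, whichever is earlier. Again there is no lag.
- **The note after Echocardiogram in section 8.2.6** lists the safety outputs it governs. Deaths is on the list and Survival is not. It says "all events collected till last tafamidis dosing date +28 days will be summarized for the tafamidis treated set and its associated sub-sets".
- **Section 8.2.6, Exposure** plans an exposure-adjusted mortality rate for the treated set. Exposure time is the "Sum of all non-missing days when tafamidis was taken", with trial and compassionate-use days removed. The paragraph gives no event window of its own.

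The Kaplan-Meier analysis and the Deaths summary cover the same treated sets: overall, by phenotype, severe hepatic impairment, and liver transplant status. Medians and "95% CIs if the number of events are at least 5" are promised under Survival Analyses. Section 8.1 gives the same condition for Kaplan-Meier estimates generally: "if the number of events are at least 5".

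For the untreated set, section 5.2 says "Available data after a patient discontinues treatment with tafamidis will be excluded".

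**The concern.** Two outputs in one report describe mortality in the same patients under different end dates, and no visible text explains why. A reader who compares the number of deaths with the number of Kaplan-Meier events would find that they disagree.

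The direction matters as well. The SAP introduction says the data will inform the effect of tafamidis on survival. If some patients stop the drug because they are dying, censoring at the last dose removes those deaths and raises the treated curve. Section 5.2 keeps those deaths out of the untreated curve too. The all-enrolled part of the Deaths summary still holds them ("whether deaths were ATTR related will be provided using all enrolled patients"), but that is a count and not a survival estimate.

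The five-event rule adds a reporting effect: the choice of window can decide whether a small treated subset gets a survival estimate at all.

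**Working it through.** The plan states no event count, rate or sample size for survival, so there is no figure to reproduce. The first step needs no assumption. The later steps rest on assumed inputs and are illustrative.

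**1. The rules applied to a death d days after the last dose.** Under section 6.2.1 it is a Kaplan-Meier event if d ≤ 0. Under the note it is counted if d ≤ 28.

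| d | Kaplan-Meier | Deaths summary (treated set) |
|---|---|---|
| 0 | event | counted |
| 1, 10, 28 | censored | counted |
| 29 | censored | not counted |

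Every death on days 1 to 28 is classified differently.

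**2. Stopping unrelated to prognosis.** With stopping rate c per year and Δ = 28/365.25 = 0.0767 years, the share of counted deaths lying in the gap is about cΔ/(1 + cΔ). For c = 0.05, 0.10 and 0.20 this is 0.38%, 0.76% and 1.51%. The outputs disagree slightly, but the curve is not biased.

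**3. Stopping shortly before death.** Let a fraction p of on-drug deaths follow a stop 1 to 28 days earlier. Censoring them multiplies the event hazard by (1 − p), so the curve estimates S^(1−p). A product-limit simulation (400,000 patients per scenario, stopping at 5, 10 or 20% per year, administrative censoring uniform over 1 to 10 years) agrees.

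| p | True 80%: formula | simulated | True 60%: formula | simulated |
|---|---|---|---|---|
| 5% | 0.80^0.95 = 80.9% | 80.9–81.1% | 0.60^0.95 = 61.6% | 61.5–61.7% |
| 10% | 0.80^0.90 = 81.8% | 81.7–81.9% | 0.60^0.90 = 63.1% | 63.1–63.2% |
| 20% | 0.80^0.80 = 83.7% | 83.6% | 0.60^0.80 = 66.5% | 66.3–66.5% |

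The 28-day rule gave 79.9–80.2% and 59.9–60.1%. It recovers the true value only because every prognosis-related stop was placed within 28 days of death.

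**4. Five-event rule.** With exactly 5 counted deaths, the chance that fewer than 5 are Kaplan-Meier events is 1 − (1 − p)^5, or 23%, 41% and 67% for a gap share of 5, 10 and 20%. With 6 counted deaths it is 1 − (1 − p)^6 − 6p(1 − p)^5, or 3%, 11% and 35%. At the shares in step 2, with 5 deaths, it is about 2 to 7%.

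**5. Mortality rate.** Assume 10% stopping per year, 10% of deaths in the gap and true 5-year survival of 80%. The rate per 100 patient-years is 4.02 with deaths to last dose over on-drug days, 4.49 with deaths to 28 days over on-drug days, and 4.46 with both extended to 28 days.

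**6. Imputed dates.** Section 7 imputes the 1st "For dates with missing days but not missing months". It makes a separate rule for a missing tafamidis start day but does not mention the last dose. Suppose the last dose falls in the month of death, its day is missing and the death date is complete. The apparent gap is then the day of the month minus 1. Over a 365-day year, 12 death dates give gap 0, 335 give 1 to 28 days (335/365 = 92%) and 18 give 29 or 30 days.

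**The case against.** **The note may already cover survival.** Survival Analyses sits under section 8.2.6, the note closes the visible text of that section, and its opening words reach back over the safety events above it. The amendment log shows the survival move and the 28-day text arriving in the same amendment. On this reading the deaths would not be censored in the curve, and the mortality rate under Exposure would have an event window. This is a fair reading, so it cannot be said as settled fact that such deaths will be censored. But the note would then contradict sections 6.2.1 and 5.3 directly, and the text still needs reconciling.

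**The two windows may be deliberate.** The last-dose cut agrees with section 5.3, and 28 days agrees with the minimum safety reporting period in protocol section 11.2. An on-treatment curve and a safety-window count are different quantities. That is defensible, but the SAP does not say so and does not label the curve as on-treatment.

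**The bias figures are assumed.** This stands. A reader might infer that treated survival will be overstated by several points, or that a 28-day window would cure it. The documents support neither. With stopping unrelated to prognosis there is no bias. If decline leads to stopping earlier than 28 days before death, the longer window does not remove the bias.

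**The threshold and imputation effects are narrow.** This also stands. Step 4 conditions on a count of 5 or 6 deaths. Step 6 needs a particular pattern of missing dates; if both days are missing in the same month, both become the 1st and no gap arises. A subset that loses its curve still has its deaths in the summary and in the treated-set listing.

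**Conclusion.** The inconsistency holds in the current text on either reading: two outputs that disagree, or a note that contradicts sections 6.2.1 and 5.3. That conclusion needs no assumption.

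The size of any effect on the treated curve is unknown. It ranges from none, if stopping is unrelated to prognosis and last-dose dates are complete, to roughly 1 to 6 percentage points at 5 years under the assumed gap shares of 5 to 20%. The direction, if there is an effect, is optimistic.

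A reader might also infer immortal time, because section 6.2.1 starts the clock at first dose without qualification for patients already on tafamidis at consent. Section 5.3 and Appendix 2 point to a start no earlier than enrollment. The problem would arise only if survival were programmed from the first-ever dose without delayed entry. This is a clarification and not a finding.

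Severity is modest. Section 4 states that there are no hypotheses and that all analyses are descriptive, so the harm is inconsistent and possibly optimistic reporting, not a wrong test.

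**What to change.** 1. State one end date for treated-set mortality and use it in sections 5.3 and 6.2.1, the Deaths summary and the mortality rate under Exposure. Last dose plus 28 days, capped at end of THAOS follow-up, matches the note and protocol section 11.2. Label the curve on-treatment, and say whether person-time in the mortality rate runs to the same date. Changing section 6.2.1 alone would leave it at odds with section 5.3. If different windows are intended, say so and give the reason.
2. Add one secondary sensitivity curve for the treated set that counts all deaths to end of THAOS follow-up regardless of discontinuation. It addresses stops more than 28 days before death. State that it includes off-drug time, which is why it stays secondary.
3. As clarifications, state that the treated clock starts at the later of consent and first dose, and say in section 7 whether the 1st-of-month rule applies to the last-dose date.

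The cost is a few SAP sentences and one extra curve. No new data are needed: footnote b of SAP Table 2 says deaths are collected independently of the visit schedule.
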